8.1.2 Rescue Therapy

The need for rescue therapy including the site requiring therapy, the date and study day, the pocket depth (PD), whether SRP was performed, the protocol version under which the subject was enrolled, and any associated comments will be presented in a listing.

Additionally, a table will be created to summarize and compare the need for and timing of rescue therapy across the three treatment groups.

Further ad-hoc exploratory analyses to examine the characteristics of subjects receiving rescue therapy and the circumstances surrounding the need for rescue therapy may be conducted.

8.1.2.1 Amendment to Protocol Rescue Criteria

In this study, rescue therapy was intended to occur only after the Day 90 evaluation. However, under early versions of the protocol, the timing of rescue therapy was not explicitly stated, and rescue therapy was permitted at any time after the initial SRP treatment if indicated by clinical parameters (PD or CAL). A subsequent amendment to the protocol (Amendment 2) was made to correct this issue, but some subjects enrolled under the earlier versions of the protocol received "premature" rescue therapy prior to Day 90.

Pockets/teeth that are "rescued" should be considered treatment failures after rescue. For this reason, rescued teeth/pockets will be assigned a value equal to the worst score observed at any previous visit for that pocket/tooth in the primary and secondary analyses..

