At each evaluation, medical and dental history will be updated, an oral exam will be performed, and AEs and SAEs will be assessed and recorded. PD, CAL, and BOP will be evaluated at screening and on Days 15, 30, 60, 90, 180, and 270. Subjects will have urinalysis in addition to blood tests including hematology and chemistry (liver and kidney function) panels done at screening and repeated at Days 90 and 270. FMPI will be recorded at baseline and on Days 15, 30, 60, 90, 180, and 270. Inflammatory cytokines in serum will be measured at baseline and on Days 15, 90, 180, and 270. GCF will be collected and analyzed at baseline and on Days 15, 90, 180, and 270. Microbial analysis of periodontal flora will be performed at baseline and on Days 15, 90, 180, and 270.

At each treatment visit, in addition to administration of ST266 or placebo, medical and dental history will be updated, AEs and SAEs will be assessed and recorded, concomitant medications will be recorded, and oral hygiene instruction will be provided.

Randomization will be stratified by site and smoker status (never smoked or quit smoking more than two years ago vs. has smoked within the last two years). Randomization will be blocked such that assignment to treatment groups both within sites and within smoker status will be

approximately even (1:1:1). ST266 will be supplied to the study site and prepared for use by trained clinical staff, who will not be the same as the dental professionals evaluating the subjects.

**Primary Endpoint:** The primary effectiveness endpoint of this study is the average change in PD from baseline to 9 months (Day 270) in tooth-sites with baseline PD  $\geq$  6mm. This endpoint will be analyzed at the patient level similar to other studies.

**Secondary Endpoints:** Secondary efficacy endpoints of this study are: (1) change from baseline in CAL at 9 months (Day 270) with baseline PD  $\geq$  6mm; (2) change from baseline in BOP at 9 months (Day 270) using whole-mouth average, and (3) change from baseline in PD at 9 months (Day 270) using all tooth-sites.

Baseline refers to the initial measurement of the endpoint, which may occur at the screening or baseline visit according to the schedule of assessments.

**Safety Endpoints:** The safety endpoints are frequency and pattern of AEs and SAEs.

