## 7.4. Rescue Therapy

If at Day 90 or later a subject experiences progression of periodontitis in any tooth, rescue therapy will be provided. Progression of periodontitis is defined as an increase of 2 mm or more in PD or CAL from the baseline measurement (Goodson, 1982). Rescue therapy will consist of

the standard of care therapy at the tooth site where progression of periodontal disease occurred. Rescue therapy at the tooth site may occur immediately at the scheduled visit, or as soon as the investigator determines is reasonable to ensure the subject receives standard of care therapy.

Subjects that receive rescue therapy will continue to participate in all remaining study visits through study completion.

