## 11. ASSESSMENT OF EFFICACY

### 11.1. Criteria for Primary and Secondary Efficacy Endpoint Evaluations:

- a. Pocket Depth (PD): Periodontal pocket depth will be determined with a UNC-15 periodontal probe at 6 sites per tooth, and rounded to the next lower whole millimeter.
- b. Clinical Attachment Level (CAL): The measurement of the position of the soft tissue in relation to the cemento-enamel junction (CEJ) that is a fixed point, using probing depth and the distance from the gingival margin to the CEJ.
- c. Bleeding On Probing (BOP): Dichotomous score of 0 or 1 indicating whether the site bleeds upon probing is performed independently of the gingival index measurement. Bleeding on probing will be measured from the 6 sites of the tooth as a secondary periodontitis variable:

0 = No bleeding

1 = Bleeding within 15 seconds following probing

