8.3.1 Primary Efficacy Analyses

The generalized estimating equations (GEE) method with a linear link and exchangeable covariance matrix (within subject correlation structure) will be used to estimate the treatment group effects with respect to change from baseline PD at 270 days, adjusted for baseline PD in tooth-sites with baseline PD ≥ 6 mm. The two primary hypotheses to be tested are:

- 1) The change in PD from baseline (PD ≥ 6 mm) (Screening Visit) at the 270 Day Visit differs between the Group 1 (see section 2.4) and Group 3 (placebo) treatments. Point estimates and 95% confidence intervals will be presented for the

treatment group differences in PD change from baseline at Day 270 by baseline smoker status.;

- 2) The change in PD from baseline (PD ≥ 6 mm) (Screening Visit) at the 270 Day Visit differs between the Group 2 (see section 2.4) and Group 3 (placebo) treatments. Point estimates and 95% confidence intervals will be presented for the treatment group differences in PD change from baseline at Day 270 by baseline smoker status.

SAS code for the GEE model is as follows:

```
proc gee data=Day270dataset
  where (base $\geq$ 6 and ITT Set='Y' and paramcd='PDEPTH');
  class subjid trt01a site smoker_status;
  model chg = trt01a base site smoker_status smoker_status*trt01a;
  repeated sub=subjid /type=exch;
  lsmeans trt01a/pdiff;
run;
```

Where:

- 1) The Day270dataset only includes records for Day 270 visit)
- 2) chg = change from baseline of each individual tooth site
- 3) (base \geq 6 and ittf1='Y' and paramcd='PDEPTH'): subsets the dataset to include only PD outcomes, the ITT population, and tooth sites with baseline PD greater or equal to 6mm.
- 4) chg= change in PD from baseline
- 5) trt01a = treatment group
- 6) site=investigator institution rather than tooth site
- 7) base = baseline PD

The 15-, 30-, and 60-Day visits were not included in the primary statistical model since the tooth-sites at the earlier visits may still be healing from the effects of the SRP procedure with possible SRP-related gingival swelling affecting the PD measures.

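### The rescue rule looks only at earlier visits, so a pocket rescued before Day 270 and deeper still at Day 270 is scored better than measured

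*SAP*

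**What the plan says.** SAP 8.1.2.1 states the purpose first: rescued pockets or teeth "should be considered treatment failures after rescue". It then gives the rule for the primary and secondary analyses: "rescued teeth/pockets will be assigned a value equal to the worst score observed at any previous visit for that pocket/tooth". It does not say whether earlier means before the rescue or before the analysis visit, or whether the rescue visit's own reading counts. It also does not say what happens when the current reading is the worst.

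Protocol 7.4 sets when rescue happens: "If at Day 90 or later a subject experiences progression of periodontitis in any tooth, rescue therapy will be provided". The trigger is given as "Progression of periodontitis is defined as an increase of 2 mm or more in PD or CAL from the baseline measurement". On timing, "Rescue therapy at the tooth site may occur immediately at the scheduled visit", or later at the investigator's judgement. The same section keeps rescued subjects in the remaining visits. SAP 8.1.2.1 adds that some subjects enrolled under early protocol versions were rescued before Day 90.

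On measurement, Protocol 7.1 says "PD, CAL, and BOP will be evaluated at screening and on Days 15, 30, 60, 90, 180, and 270", and Protocol 11.1 has PD "rounded to the next lower whole millimeter". On the primary model, SAP 8.3.1 says "The Day270dataset only includes records for Day 270 visit". For a rescued pocket, the assigned value therefore stands in for the Day 270 reading.

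**The concern.** A rule meant to score failures should never give a pocket a better value than the one measured. This rule can, because it discards the Day 270 reading without checking whether that reading is the worst.

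The SAP's other conservative rules do not share the problem. For a missing pocket (SAP 8.1.1) the worst earlier value is used because no current reading exists. For visits after discontinuation, the worst observation for each pocket is carried forward. When two assessments in a window tie (SAP 8.1.4), the worse one is used. In the rescue rule alone, an available and worse reading is dropped.

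What is at stake is the value of a small set of the worst pockets in the primary PD analysis, in the CAL analysis and in the whole-mouth BOP percentage. A second stake is reproducibility: two programmers could build different Day 270 datasets from the same sentence.

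**Working it through.** **1. Worked pockets.** Each row lists PD in whole mm at screening and Days 15, 30, 60, 90, 180 and 270. The sequences are illustrative. Change is the value minus the screening value of 6. Assigned is the maximum over visits before Day 270, minus 6. Floor is the maximum including Day 270, minus 6.

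| Case | Readings | Rescue | Measured | Assigned | Floor |
|---|---|---|---|---|---|
| A | 6, 5, 5, 5, 6, 8, 9 | Day 180 | +3 | +2 | +3 |
| B | 6, 5, 5, 5, 6, 8, 5 | Day 180 | −1 | +2 | +2 |
| C | 6, 6, 6, 6, 6, 6, 8 | Day 270 | +2 | 0 | +2 |
| D | 6, 5, 5, 5, 6, 7, 8 | Day 270 | +2 | +1 | +2 |
| E | 6, 8, 6, 5, 5, 6, 8 | Day 270 | +2 | +2 | +2 |
| F | 6, 9, 6, 5, 5, 6, 8 | Day 270 | +2 | +3 | +3 |

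**2. Rescue before Day 270 (A, B).** Day 270 falls after rescue, so the rule applies on any reading of the text. Case B works as intended: a pocket that improved after rescue is still a failure. Case A does not, because the pocket is credited with 1 mm it did not gain. If earlier means strictly before the rescue visit, case A is assigned 6 mm, a change of 0, which is further from the measured +3.

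**3. Rescue at Day 270 (C to F).** A pocket first triggered by PD at Day 270 reads at least baseline + 2 that day. PD is in whole mm, and progression at Day 90 or 180 would already have led to rescue, so those two readings are at most baseline + 1. With no higher reading on Days 15 to 60, the literal rule assigns 0 or +1 (C, D). If screening does not count as an earlier visit, 6, 5, 5, 5, 4, 5, 8 is assigned −1. An early peak as high as Day 270 removes the understatement (E), and a higher peak reverses it (F). If rescue was triggered by CAL alone, PD may be unaffected.

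**4. Scale.** The plan's sample size comes first: difference 0.5 mm, SD 0.7 mm, two-sided alpha 0.025, power 85% (SAP 2.6 and 3).

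n = 2 × [0.7 × (2.241 + 1.036) / 0.5]² = 42.1, so 43 by the normal approximation. The noncentral t gives exactly the plan's 44. The figure is reproduced and not in dispute.

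If a share f of an arm's eligible pockets is understated by u mm, the arm mean shifts by about f × u. The group difference shifts by (f placebo − f ST266) × u. Values of f and u are assumptions, since the documents give none. Power is by the normal approximation at 44 per group, with a standard error of 0.7 × √(2/44) = 0.149 mm and a true difference of 0.5 mm.

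| f placebo | f ST266 | u (mm) | Shift (mm) | Power |
|---|---|---|---|---|
| 1% | 1% | any | 0 | 86.6% |
| 2% | 1% | 1 | 0.01 | 85.1% |
| 5% | 1% | 2 | 0.08 | 71.7% |
| 10% | 2% | 3 | 0.24 | 30.9% |

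The last row is an outer bound, not an expectation. The table treats an arm mean as a simple average over pockets; the GEE weights differ somewhat.

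**The case against.** The strongest reply is that the sentence before the rule limits failure status to the time after rescue and offers this as the reason for the substitution. A Day 270 reading that triggers a rescue is taken before it. On that reading the value stays at baseline + 2 mm or more, and cases C and D are not distorted. Rescue may also follow the last study reading altogether, because Protocol 7.4 allows it to be given later and Day 270 is the final visit. This stands. A reader might infer that every pocket rescued at Day 270 is scored too well, but the documents do not support that. Even on the literal reading, early peaks and CAL-only triggers are exceptions. What remains for Day 270 rescues is an ambiguity.

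A second reply is that the effect is negligible. To be affected, a pocket must progress after SRP, be rescued, and then be deeper than at every earlier visit. That is plausibly rare, and if the arms are affected equally the group difference does not move. This is a fair reason to rank the point low. It does not make the rule correct, and it does not touch case A, which holds on either reading of the text.

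**Conclusion.** The point holds as a minor defect in the analysis rule. For a pocket rescued before Day 270 and deeper still at Day 270, the SAP assigns a better value than the one measured, against its own stated aim. For a pocket rescued at Day 270, the SAP supports two readings that give different values.

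The size cannot be derived from the documents, which give no rescue rates, probing error or pocket trajectories. A small effect is most likely: 2% against 1% of pockets, 1 mm each, moves the difference by 0.01 mm, or 2% of the planned 0.5 mm. Larger shifts need a marked imbalance between arms.

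A reader might also infer that the rule always pulls the arms together. It does so only if affected pockets are commoner on placebo. If they are commoner on ST266, it flatters ST266. Nothing in the documents settles which.

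**What to change.** Replace the assignment sentence in SAP 8.1.2.1 with:

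> For every analysis visit at or after rescue, a rescued pocket/tooth takes the worst score recorded at any visit up to and including that analysis visit. A reading taken at the rescue visit before rescue counts as recorded.

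Apply the same floor to PD, CAL and BOP. It never gives a better score than the measured one, it keeps case B as a failure, and it gives one answer for rescues at Day 270 (the Floor column above).

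The cost is one sentence and one line of programming. One consequence should be accepted openly. A pocket rescued at Day 270 keeps any higher early reading (case F, +3), although SAP 8.3.1 warns that early readings may reflect swelling after SRP. The literal rule already does this; the after-rescue reading would not. SAP Section 1 places the plan before database lock and any analysis of the primary endpoint, so the change can be prespecified while that remains true. It alters how rescued pockets are analysed and leaves the rescue criteria as they are.

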
Duration of Treatment:
 
Group 1: ST266 dosed daily on Days 1-5, 8-12, 22, and 30, and then monthly for 7 months (Days 60, 90, 120, 150, 180, 210, and 240).
 
Group 2: ST266 dosed 2x/week (with at least one day between treatments) for the first 3 months and monthly for 5 months thereafter (Days 120, 150, 180, 210, and 240).
 
Group 3: Placebo dosed at the same frequency as Group 1.

Placebo, Dosage, and Mode of Administration: Sterile saline (0.9% NaCl) will be applied in the same manner and in the same volume as the investigational product, ST266.

Criteria for Evaluation:
 
Efficacy:
 
The primary efficacy endpoint of this study is the change from baseline in the PD for each patient at 9 months (Day 270) for those pockets ≥ 6mm at baseline.
 
Secondary efficacy endpoints of this study are:
 
(1) Change from baseline in CAL at 9 months and (2) change from baseline in BOP at 9 months for those pockets ≥ 6mm at baseline.
 
Exploratory endpoints of this study are:
 
(1) Pro-inflammatory mediators, enzymes and bone markers will be measured in gingival crevicular fluid (GCF) and serum at the baseline, Days 15, 90, 180, and 270;
 
(2) Microbial analysis of periodontal flora will be performed at baseline and at Days 15, 90, 180, and 270; and
 
(3) Change from baseline in radiographic bone levels (RBL) at Days 90 and 270. PD, CAL, BOP, and FMPI will also be summarized at Days 90, 180 and 270.
 
(4) Smoker/treatment interaction will be summarized for PD and CAL at Days 90, 180, and 270.
 
(5) Percent of patients with all pockets < 5mm will be summarized at Days 90, 180 and 270.
 
(6) Percent of patients with pockets decreasing by 2mm or more that at baseline were ≥ 5mm will be summarized at Days 90, 180 and 270.
 
(7) Percent of patients with 75% of pockets < 5mm that at baseline were ≥ 5mm will be summarized at Days 90, 180 and 270.
 
Safety: The safety endpoints are frequency and pattern of adverse events (AEs) and serious adverse events (SAEs).

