2.1 Study Objectives

The primary objective is to estimate the efficacy of ST266 to reduce pocket depth (PD) as an adjunctive to scaling and root planing (SRP).

The secondary objectives of this study are to determine: (1) safety as established by assessment of AEs and SAEs, and (2) changes in the following clinical parameters:

- Clinical attachment level (CAL)
- Bleeding on probing (BOP)

Additional exploratory objectives are to compare the effects of the treatments and dosing schedules in the following:

- Proinflammatory mediators, enzymes, and bone markers in gingival crevicular fluid (GCF) and serum
- Periodontal flora as determined from microbial analyses
- Radiographic bone level (RBL)
- Full-mouth plaque index (FMPI)
- Percent of patients with all pockets < 5mm
- Percent of patients with pockets decreasing by 2mm or more that at baseline were ≥ 5 mm
- Percent of patients with 75% of pockets < 5mm that at baseline were ≥ 5 mm

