8.3.4 Exploratory Efficacy Analyses

FMPI will be analyzed using the GEE method described in section 8.3.1 at days 90, 180, and 270. Additionally, CAL change from baseline at days 180 and 270 using all tooth-sites will be analyzed using GEE. PD change from baseline at days 90, 180, and 270 using a whole-mouth average will be analyzed using ANCOVA with the model described previously.

Analysis methods for the exploratory efficacy outcomes, (1) inflammatory cytokines in GCF and serum, (2) microbial periodontal flora and (3) RBL will be described in a separate statistical analysis plan.

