8.5 Exploratory Categorical Analysis of PD

In addition to analyzing PD as continuous variable, it is often useful to analyze PD categorically. The following may also be summarized descriptively:

- Percent of subjects in each group with a mean PD change from baseline <-4mm, <-3mm, <-2mm, <-1mm, -1mm to 1mm, >1mm, >2mm, >3mm, >4mm at 90, 180 and 270 days
- Percent of subjects with pockets decreasing by 2mm or more that at baseline were < 5mm at 90, 180, and 270 days.
- Percent of tooth sites in each group with a mean PD change from baseline <-4mm, <-3mm, <-2mm, <-1mm, -1mm to 1mm, >1mm, >2mm, >3mm, >4mm at 90, 180 and 270 days
- Percent of subjects in each group with a mean PD <5mm, <6mm and < 7mm at 90, 180 and 270 days
- Percent of subjects in each group with all PD <5mm, <6mm and < 7mm at 90, 180 and 270 days
- Percent of subjects with 75% of pockets < 5mm that at baseline were < 5mm at 90, 180, and 270 days.
- Percent of tooth sites in each group with a mean PD <5mm, <6mm and < 7mm at 90, 180 and 270 days
- Percent of subjects in each group with PD <5mm at day 90 by baseline PD

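### The SAP calls rescued pockets treatment failures but gives no rescue rule for the exploratory responder endpoints, so post-rescue readings can enter them as observed

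*SAP*

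**What the plan says.** SAP 8.1.2.1 makes two statements. The first is a principle with no restriction by analysis: rescued pockets or teeth "should be considered treatment failures after rescue". The second puts it into operation: they "will be assigned a value equal to the worst score observed at any previous visit for that pocket/tooth in the primary and secondary analyses".

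The SAP's primary and secondary endpoints (Section 2.2, Table 8-1) are PD and CAL at Day 270 in sites with baseline PD of 6 mm or more, and whole-mouth BOP. The patient-level responder criteria are exploratory. Section 2.1 introduces them with "Additional exploratory objectives are to compare the effects of the treatments and dosing schedules in the following", and Section 2 says "Percent of patients with all pockets < 5mm will be summarized at Days 90, 180 and 270". The other two criteria concern pockets of at least 5 mm at baseline: a decrease of 2 mm or more, and 75% of such pockets falling below 5 mm. Section 8.5 adds descriptive categories, such as "Percent of subjects in each group with all PD <5mm, <6mm and < 7mm at 90, 180 and 270 days". Section 8.3.4 adds all-site CAL and states "PD change from baseline at days 90, 180, and 270 using a whole-mouth average will be analyzed using ANCOVA with the model described previously". None of these carries a rescue rule.

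Protocol 7.4 triggers rescue, from Day 90 on, when PD or CAL at any tooth has risen by 2 mm or more from baseline. Treatment is given at the site that progressed, and the subject stays in the study for all remaining visits.

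**The concern.** The failure principle is general, but the rule that enforces it is not. A pocket that progressed and was rescued can carry its worst score in one table and its treated value in another table of the same report. Two contrasts show the inconsistency:

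- For a site below 6 mm at baseline, BOP takes the worst score (whole-mouth BOP is secondary), while PD can enter the responder tables as observed.
- The worst-value rule for missing data in SAP 8.1.1 is not limited to any level of analysis. A dropout therefore keeps the worst value in the exploratory tables, while a rescued pocket may not.

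What is at stake is the responder comparison. If ST266 works, rescue should be more frequent on placebo. Crediting the effect of rescue as response would then raise the placebo rate more than the ST266 rate and shrink the apparent difference.

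**Working it through.** **1. Rule against endpoint status.**

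| Analysis | Protocol | SAP | Rescue rule |
|---|---|---|---|
| PD, sites ≥ 6 mm, Day 270 | primary | primary | worst score |
| CAL, sites ≥ 6 mm; whole-mouth BOP | secondary (7.1) | secondary | worst score |
| All-site / whole-mouth PD, Day 270 | secondary (synopsis, 7.1) | exploratory (8.3.4) | depends on document |
| Three responder criteria | not listed | exploratory (2, 2.1, 2.2) | none stated |
| Categories in 8.5 | not listed | descriptive | none stated |
| All-site CAL | not listed separately | exploratory (8.3.4) | none stated |

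**2. Does another rule fill the gap?** SAP 8.1.1 covers missing readings, but rescued subjects keep attending, so theirs are observed. SAP 8.1.4 admits in-window assessments to the analysis. SAP 8.3.3 carries the primary and secondary technique to other time points, so those analyses arguably inherit the rule; the responder criteria do not.

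**3. Example.** A pocket is 5 mm at screening and 7 mm at Day 90 (+2 mm, which meets the protocol's progression definition). It is rescued and reads 4 mm at Day 270. As observed it passes the below-5 mm test; with its worst score (7 mm) it fails.

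**4. Size for responders.** The documents give no rescue rate, so there is no figure of the plan's own to reproduce. Let *r* be the share of an arm that is rescued, and *q* the share of rescued patients who meet the criterion only because of post-rescue readings, taken as equal across arms.

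Inflation in an arm = *r* × *q*. Shift in the difference = *q* × (*r*placebo − *r*active).

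| Assumed *r*, placebo / active | *q* = 10%: placebo, active, shift (points) | *q* = 50%: placebo, active, shift (points) |
|---|---|---|
| 10% / 5% | 1.0, 0.5, **0.5** | 5.0, 2.5, **2.5** |
| 20% / 10% | 2.0, 1.0, **1.0** | 10.0, 5.0, **5.0** |
| 30% / 15% | 3.0, 1.5, **1.5** | 15.0, 7.5, **7.5** |
| 30% / 10% | 3.0, 1.0, **2.0** | 15.0, 5.0, **10.0** |

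The range of 0.5 to 10 points belongs to these pairs. Pairing the extremes freely gives 0.50 × (0.30 − 0.05) = 12.5 points at one end. If rescue were more frequent on ST266, the sign reverses: 0.50 × (0.10 − 0.15) = −2.5 points.

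**5. Size for whole-mouth PD.** Assume a rescued site with worst change +2 mm and post-rescue change −2 mm, a gap of 4 mm. At six sites per tooth, 18 teeth (the entry minimum) give 108 sites; 28 teeth (assumed) give 168. One such site moves the patient's mean by 4/108 = 0.037 mm or 4/168 = 0.024 mm. With 1 to 6 rescued sites per rescued patient and a 10 to 20 point gap in rescue rates, the between-group shift runs from 0.10 × 1 × 4/168 = 0.002 mm to 0.20 × 6 × 4/108 = 0.044 mm.

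**6. Would the worst score alone be enough?** Not for the all-pockets criterion. A site going from 2 to 4 mm meets the +2 mm trigger, yet its worst score of 4 mm is still below 5 mm. Rescue triggered by CAL need not raise PD at all. For the two criteria restricted to pockets of at least 5 mm at baseline, the worst score does ensure failure of the pocket, because the screening value counts as a previous visit.

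**The case against.** The strongest reply is that the SAP is silent here. The principle in 8.1.2.1 is unrestricted, and a programmer could apply it everywhere. A reader might infer that the plan counts post-rescue readings as success. The documents do not say that: as-observed use is the natural reading of an expressly limited rule, not a stated one, and a reading helps only if it meets the threshold. What stands is that the handling is not pre-specified.

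Three other strong readings also fail:

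- Whole-mouth PD is a mean and has no success category. Under the protocol's classification the rule may already reach it.
- It is tempting to say that sites below 6 mm are seen only by the exploratory endpoints. Whole-mouth BOP covers them too, and it is secondary.
- A firm figure for understated benefit is not available. Multiplying the share rescued by the share who then respond treats every rescued responder as false. For the all-pockets criterion every other pocket must also be below 5 mm, in patients who entered with at least six teeth at 6 mm or more, so *q* may be small.

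Some mitigation exists. SAP 8.1.2 requires a rescue listing by site and date and a table comparing rescue across arms. The responder items are summaries with no test specified. Under the current protocol rescue starts at Day 90, so Day 90 results are affected mainly by the premature rescues that 8.1.2.1 records. Observed values in exploratory tables can also be a legitimate choice, but the SAP would have to say so, and it would have to square with its own failure principle.

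**Conclusion.** The point holds as a gap in the rescue rule. The SAP's failure principle is not carried into the exploratory responder endpoints, the 8.5 categories or all-site CAL, and as written post-rescue readings can enter them. Under the assumed pairs of rescue rates and *q* of 10–50%, the between-arm responder difference shifts by about 0.5 to 10 points. It shifts against ST266 only if rescue is more frequent on placebo. For whole-mouth PD the shift is about 0.002 to 0.044 mm, and the disagreement between protocol and SAP on that endpoint's status matters more than the size. The primary analysis and the SAP's secondary analyses are untouched, so this is a minor but worthwhile correction.

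**What to change.** - Extend the last sentence of SAP 8.1.2.1 to all PD, CAL and BOP analyses, naming 8.3.4, 8.5 and the responder endpoints of Sections 2, 2.1 and 2.2.
- For the responder endpoints, score any pocket rescued before the visit as not meeting its pocket-level criterion. A patient with such a pocket then cannot count under the all-pockets criterion, but could still meet the 75% criterion on the other pockets.
- Show as-observed results as a sensitivity summary.
- Reconcile the status of all-site PD between the protocol (secondary) and the SAP (exploratory).
- While editing, align the baseline subset of the two restricted criteria: Section 8.5 has below 5 mm where Sections 2, 2.1 and 2.2 have 5 mm or more. Also state how many pockets must decrease by 2 mm, since the effect of a rescued pocket depends on it.

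The cost is a few lines of SAP text and one derived flag, from rescue data that SAP 8.1.2 already lists by site and date. Responder rates become slightly lower in all arms. The change belongs before database lock and unblinding.
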